## 1. Background

---

Approximately 9000 patients are treated for head and neck cancer (HNC) by the NHS every year (Paleri et al 2018). There has been a dramatic increase in oropharyngeal cancer (OPC) over the past 15 years and this in part is due to the rise in Human Papilloma Virus (HPV) related disease (Schache et al 2016). Non-HPV related OPC, which is traditionally associated with a history of smoking and alcohol, is also increasing in the UK (Schache et al 2016). This trend is predicted to continue with an expected 50% rise in HNC cases over the next 20 years (Louie et al 2015).

Primary OPC is treated with curative intent using (chemo) radiation, surgery or a combination of these treatment modalities (NICE, 2016). Dysphagia is one of the most profound side-effects of HNC and/or its treatment, with swallowing ability being a priority concern for patients up to one year following treatment (Roe et al 2014). Dysphagia is an independent predictor of survival and is associated with higher risk of pneumonia, poorer oral intake, prolonged gastrostomy use, poor nutritional status and weight loss as well as fundamental changes to eating patterns, social life, and subsequent quality of life (QoL) (Patterson et al 2016). Speech can also be affected by the presence of a tumour or the treatments received in particular surgical management and this can have a devastating impact on a person's psychosocial well-being, participation in social and occupational roles and overall QoL (Clarke et al 2016).

Despite advances in various treatment modalities, the overall prognosis of HNC patients has not improved significantly within the last several decades and advanced tumours have a recurrence rate of 20–30% at the primary tumour site (Mandapathil et al 2014). Patients may present with residual disease (diagnosed within 12 months of initial treatment) or recurrent disease (diagnosed within 5 years of initial treatment) (Hardman et al, 2020). In addition to residual/ recurrent disease, patients with HNC are also over 11 times more likely than the general population to develop a second primary head and neck cancer (Chuang et al 2008). For patients with second primary HNC disease, this typically occurs in a previously irradiated field including the primary disease site and/or neck and in the radical or adjunctive setting (Hardman et al 2020). Due to the complexity of further treatment in any form, patients with residual, recurrent and new primary disease in a previously irradiated field, are considered a homogenous cohort (Paleri et al 2020) and for the purposes of this document will be referred to as patients with recurrent OPC.

Recurrent OPCs present some of the most challenging management issues in head and neck surgical and oncological practice. Surgery or re-irradiation may be the only hope for locoregional disease control however these treatments may have substantial implications for communication and swallowing function and overall QoL (Mehanna et al, 2016). As a result, the majority of these patients are either treated with palliative intent including chemotherapy, immunotherapy, clinical trial entry or receive best supportive care (Mehanna et al, 2016). However, recent literature has suggested that survival outcomes are improving for patients with recurrent OPC. A recent meta-analysis shows that the outcomes in cases of OPC recurrence appear to have improved significantly over the last two decades, reaching five-year survival of 50 per cent in patients treated surgically

(Jayaram et al, 2016). Improved survival may be the result of a combination of factors including patient selection, advances in surgical care and the role of HPV as a distinct aetiological factor (Mehanna et al, 2016).

The aim of surgical resection in the recurrent setting, also referred to as salvage surgery, is complete macroscopic clearance of the recurrent tumour with wide clear margins which can result in large defects which require reconstruction (Mehanna et al 2016). This can have a significant functional impact on communication and swallowing and overall QoL (White et al, 2013). The consequential large functional deficits must be balanced against the benefit of longer survival (Mehanna et al, 2016). Open salvage surgery for recurrent OPC has been associated with a high complication rate with 48% patients experiencing poor healing and prolonged hospital stays (Zafereo et al 2009). Successful resection of OPC recurrence can be difficult due to the complex three-dimensional anatomy and proximity and adherence to the internal carotid artery (Mehanna et al 2016). Access procedures through mandibulotomy (jaw split) or lingual release (lip split) are usually required and in the setting of previous radiotherapy this can increase the risk of osteoradionecrosis, in addition to extensive disruption to the oral cavity and floor of mouth musculature (Hamilton & Paleri, 2017). Recent advances in transoral robotic surgery (TORS) have facilitated transoral access to the oropharynx avoiding the need for mandibulotomy or lingual release (Hamilton & Paleri, 2017). The use of this minimally invasive surgical approach is now being extended to the treatment of recurrent OPC (Paleri et al 2020). A recent multicentre case control study showed that salvage patients treated with transoral robotic surgery had a significantly lower incidence of tracheostomy, feeding tube use, and shorter hospital stay, with significantly decreased incidence of positive margins and significantly higher survival than matched patients treated with open surgery (White et al 2013). Favourable outcomes in terms of swallowing recovery have also been reported (Paleri et al 2020).

In the era of highly conformal radiotherapy techniques such as intensity-modulated radiotherapy (IMRT), there may be opportunities for re-irradiation, however this is associated with toxicity and has the potential to further compound pre-existing treatment related effects including swallowing function (Brady et al, 2020).

Patients receiving best supportive care have an average overall survival of four months after diagnosis (Mehanna et al 2016). As per national guidelines, patients with non-resectable recurrent OPC being considered for palliative systemic treatments should be offered the opportunity to participate in clinical trials of new therapeutic agents (Mehanna et al 2016). Triple therapy with platinum, cetuximab and 5-fluorouracil (5-FU) (EXTREME regimen) appears to provide the best outcomes for the management of patients with recurrence who have a good performance status and are fit to receive chemotherapy (Mehanna et al 2016). In a large multisite retrospective review including 733 patients across 71 sites, for patients treated with platinum-based combinations, overall survival was 8 months (95% CI: 7.0 – 8.0), with 1-year survival reaching only 30.9% (95% CI 27.5 – 34.3) (Grünwald et al 2020). More recently, however, the results of the KEYNOTE-048 study have shown that selected patients experience better survival outcomes and less toxicity with single-agent pembrolizumab or combined pembrolizumab-chemotherapy when compared with the EXTREME regimen (Burtness et al 2019).

National guidance recommends that patients with recurrent HNC should undergo appropriate and extensive counselling regarding expected survival and functional outcomes for treatments for recurrent disease (Mehanna et al, 2016). However, empirical multidimensional functional outcome data is not available for these patients and such data may aid treatment decision making if there are particular concerns regarding function. Given ongoing advancements in the treatment options for recurrent OPC with evidence of improved survival outcomes, these patients are now living longer. However, not only are they living with the well documented treatment effects of their primary treatment (Roe et al 2014), these difficulties are now potentially compounded and exacerbated by further radical surgery, re-irradiation or systemic and targeted therapies.

## 2. Rationale

---

To enable people to make informed choices about the range of treatments available for recurrent OPC, detailed information is required on the likely trajectory of functional and QoL change during or following treatment. Patient experience data is essential for any research so that relevant QoL endpoints can be identified, appropriate outcome data can then be collected and thus meaningful data can be presented to patients during the decision-making process (Blanchard et al 2016). This project will aim to address the gaps in the literature with regards to both functional and QoL outcome data and patient/ carer experience of the functional changes in communication and swallowing and overall QoL during and following treatments for recurrent OPC.

The purpose of this study is to understand the lived experience of being diagnosed and living with recurrent head and neck cancer and how functional and QoL changes are prioritised by patients. This study will also measure the trajectory of swallowing, communication and QoL change for people undergoing treatments for recurrent OPC.

## 3. Aims

---

1. To report on functional and QoL outcomes for patients who undergo treatments for recurrent OPC including surgery (open or TORS), re-irradiation, palliative systemic or targeted therapies.
2. To describe patient and carer experience of recurrent OPC and priority concerns with regards to function and QoL.

## 4. Study Design

---

This study is an exploratory observational design.

This study will comprise of two work streams including:

1. Part A: prospective non-randomised, non-interventional descriptive observational cohort study
2. Part B: a non-interventional, non-randomised longitudinal qualitative descriptive interview study using thematic analysis

Please see figure 1 for study schema.

### Population

Part A: patients with biopsy proven residual, recurrent or new primary OPC in a previously irradiated field.

Part B: patients with biopsy proven residual, recurrent or new primary OPC in a previously irradiated field, and their carers.

## 5. Study objectives

---

[figure not shown]
The primary objective of the study is to measure change in swallowing function over time for patients receiving treatment for recurrent OPC which will be evaluated by a patient-reported outcome (PRO) using the MD Anderson Dysphagia Inventory (MDADI) (Chen et al 2001) comparing change from baseline to 6 months.

Secondary objectives for the study are to:

1. Investigate potential changes in function for up to 6 months using
  - (i) The Performance Status Scale for Head and Neck Cancer (PSS- HN) scale (normalcy of diet, eating in public and understandability of speech scales) (List et al 1990)
  - (ii) the 100 mL Water Swallow Test (100ml WST) (Patterson et al 2011)
  - (iii) the International Dysphagia Diet Standardisation Initiative (IDDSI) functional diet score (Steele et al 2018)
  - (iv) Fibreoptic Endoscopic Evaluation of Swallowing Dynamic Imaging Grade of Swallowing Toxicity (FEES DIGEST) grade (Starmer et al, *in press*)
2. Assess patient-reported QoL and priority concerns using the University of Washington Quality of Life (UW-QoL) questionnaire (v.04) (Rogers et al 1999)

3. Assess patient-reported priority concerns at baseline and 6 months using the Chicago Priority Scale (CPS) (Sharp et al 1999)
4. Report on gastrostomy tube usage up to 6 months
5. Report on survival status up to 6 months
6. To explore patient and carer priority concerns with regards to function and QoL and how these concerns may influence decision making regarding treatment options using semi structured interviews

**Figure 1: Study schema**

## 6. Study end points

Primary and secondary endpoints for Part A non-interventional descriptive observational cohort study are as follows:

### Primary endpoint

Difference in the mean MDADI composite score at baseline compared to 6 months after surgical treatment or re-irradiation or 6 months into non-surgical treatment

### Secondary endpoints

1. MDADI composite score at baseline and 3 and 6, months following surgical or re-irradiation treatment or 3 and 6, months into non-surgical treatment.
2. Mean PSS-HN Normalcy of diet, public eating and speech intelligibility using the PSS-HN scale scores at 3 and 6 months .
3. Median (IQR) IDDSI functional diet score International dysphagia diet standardisation initiative functional diet scale (IDDSI-FDS) at baseline and 3 and 6 months following surgical or re-irradiation treatment or 3 ad 6,months into non-surgical treatment.
4. Mean 100ml WST capacity score score at baseline and 3 and 6, months following surgical or re-irradiation treatment or 3 and 6 months into non-surgical treatment.
5. FEES DIGEST summary score at baseline and 3 and 6 months following surgical or re-irradiation treatment or 3 and 6months into non-surgical treatment.
6. Mean UW-QoL4 composite physical, social and functional scores at baseline and 3 and 6 months following surgical or re-irradiation treatment or 3 and 6 months into non-surgical treatment.
7. Number and percentage of patients ranking of CPS categories (1-12) in order of importance, at baseline and 6 months following surgical or re-irradiation treatment or 6 months into non-surgical treatment
8. Number and percentage of patients still alive at the end of the study
9. Number and percentage of patients using a gastrostomy at each time point at baseline and 3 and 6 months following surgical or re-irradiation treatment or 3 and 6 months into non-surgical treatment.

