### **Part A**

Following informed consent, patients will have all functional and QoL measures collected at their next scheduled outpatient appointment. No additional outpatient appointments or patient contacts will be required for RM patients. All patients are routinely seen by the clinical team at baseline, and for regular follow up including 3 and 6 month clinical reviews, where all measures except the Chicago Priority Scale (CPS) will be repeated. The CPS will be completed at baseline and 6 months only. In the event that social distancing measures remain in place and patients are not attending the hospital for face-to-face review with their clinical team, or if the patient has a preference for remote review, and for participants identified via PICs, a video consultation will be set up so that a minimum set of outcome measures can be collected including the MDADI, and UWQoL4, PSS- HN (all domains), Functional IDDSI Diet Score, CPS and the 100ml WST.

The only measure which cannot be obtained via remote means is the FEES assessment. Please see figure 2 for data acquisition schema.

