### Part A

Baseline patient characteristics (age, gender, ethnicity and previous HNC treatment history) will be summarized in addition to the diagnostic and treatment details (site of recurrence, type of treatment, use of reconstruction, tracheostomy, feeding tube presence/ type) using descriptive statistics.

The primary endpoint data will be analysed to compare the mean change from baseline MDADI composite score to 6 months into or post treatment using a two-sided paired t-test if data are normally distributed. In the event of not normally distributed data non-parametric-methods (Wilcoxon Signed Rank test) will be used.

Secondary endpoints (PSS, 100ml WST, IDDSI functional diet score, FEES-DIGEST and UW-QOL, and CPS scores) will be summarised using summary statistics (mean with standard deviation if data are normally distributed or median with IQR if data have a skewed distribution). Counts and percentages will be presented with 95% confidence intervals.

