### Procedure:

#### Timing of assessments

The PSS-HN assessment is to be carried out at the time points as specified in the protocol: at baseline, and at 3, 6, and 12 following diagnosis. The PSS-HN assessment is to be carried out after completion of the patient reported outcomes, to avoid bias on self-reporting, but before the instrumental FEES assessment.

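### Secondary objective 1 asks for change in function, but the PSS-HN endpoint omits baseline and the secondary measures are only summarised visit by visit, which can blunt or mask a decline

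*Combined protocol and SAP*

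**What the plan says.** Secondary objective 1 (Section 5) is to "Investigate potential changes in function for up to 6 months using" the PSS-HN, the 100ml water swallow test (WST), the IDDSI functional diet score and FEES-DIGEST. Section 2 gives the wider purpose: to measure how swallowing, communication and quality of life change over time, so that patients can choose between treatments.

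In Section 6 the second secondary endpoint is "Mean PSS-HN Normalcy of diet, public eating and speech intelligibility using the PSS-HN scale scores at 3 and 6 months". The neighbouring items do name baseline, for example "Mean 100ml WST capacity score score at baseline and 3 and 6, months following surgical or re-irradiation treatment", but each is a score at a visit and none is a change.

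PSS-HN data exist at baseline. Section 9 (Part A) has measures taken at baseline and then at the 3 and 6 month reviews, "where all measures except the Chicago Priority Scale (CPS) will be repeated". Table 4 agrees, and the PSS-HN procedure in Appendix 1 schedules it "at baseline, and at 3, 6, and 12 following diagnosis". (Under version 5.1 in Appendix 5, endpoint data now stop at 6 months; that is not part of this point.)

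Section 11 (Part A) says the secondary endpoints "will be summarised using summary statistics (mean with standard deviation if data are normally distributed or median with IQR if data have a skewed distribution"). For proportions, 95% confidence intervals are planned. The only paired method is the t-test or Wilcoxon signed rank test for the primary MDADI comparison. Nothing states how deaths, missed visits or incomplete pairs enter the secondary summaries.

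**The concern.** Two gaps add up. First, the endpoint for PSS-HN, the first instrument listed under the objective and the only one there that covers speech, cannot yield a change from baseline as written. Second, for the other measures the reader would have to subtract one visit's mean from another's, and those means come from different sets of patients.

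The protocol itself suggests that the difference is related to function:

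- Section 1 describes dysphagia as independently predicting survival, so patients who die before 6 months are likely to have swallowed worse at baseline.
- Appendix 3 excludes patients advised to stay nil by mouth from the WST, so the worst swallowers leave that mean.
- Section 9 says "The only measure which cannot be obtained via remote means is the FEES assessment". A patient who switches between face-to-face and remote review therefore enters or leaves the FEES group from visit to visit.

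Each route pulls later visit summaries towards better function. At stake is the accuracy of figures meant for counselling: a real decline may look smaller than it was, or not show at all.

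**Working it through.** **1. The plan's own figure.** Section 10 gives pilot MDADI means of 66.50 and 52.60 and an SD of the difference of 23.68, with two-sided alpha 5% and power 95%. The difference is 66.50 - 52.60 = 13.90. For a paired t-test, the exact noncentral t calculation gives power 0.9465 at n = 39 and 0.9515 at n = 40, so the stated 40 pairs reproduce. Adding 10% gives 40 x 1.10 = 44, as stated. The sample size is not in dispute.

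**2. Endpoint wording against collection.**

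| Measure | Visits in Section 6 | Visits collected (Table 4) | Change defined? |
|---|---|---|---|
| MDADI (primary) | baseline, 6 | baseline, 3, 6 | yes, paired test |
| PSS-HN | 3, 6 | baseline, 3, 6 | no |
| IDDSI | baseline, 3, 6 | baseline, 3, 6 | no |
| 100ml WST | baseline, 3, 6 | baseline, 3, 6 | no |
| FEES-DIGEST | baseline, 3, 6 | baseline, 3, 6 (face-to-face only) | no |
| UW-QoL | baseline, 3, 6 | baseline, 3, 6 | no |

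The gap is in the endpoint and analysis text, not in data collection.

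**3. What loss does to visit means.** Let f be the fraction lost by 6 months, R and L the baseline means of those retained and lost, and D = R - L.

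- Baseline mean of everyone: (1 - f)R + fL = R - fD.
- 6-month mean of those seen, if nobody changes: R.
- Apparent change: R - (R - fD) = fD.
- If retained patients truly change by c on average, the apparent change is c + fD. The paired mean change is c.

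**4. Illustration on a 0-100 scale (points of apparent gain, no true change).**

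| Loss f | D = 10 | D = 20 | D = 30 | D = 40 |
|---|---|---|---|---|
| 10% | 1 | 2 | 3 | 4 |
| 20% | 2 | 4 | 6 | 8 |
| 30% | 3 | 6 | 9 | 12 |
| 40% | 4 | 8 | 12 | 16 |

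The 10% row is the drop-out planned in Section 10. The other losses and all values of D are assumptions.

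**5. What the documents say about loss.** For platinum-based combinations, Section 1 reports "overall survival was 8 months (95% CI: 7.0 – 8.0") and 1-year survival of 30.9%. Taking 8 months as a median and assuming exponential survival, S(6) = 0.5^(6/8) = 0.595, so about 40% are dead by 6 months. From the 1-year figure, S(6) = 0.309^(6/12) = 0.556, so about 44% are dead. If half the cohort were like this and the rest all survived, f = 0.5 x 0.405 = 0.20. The half-and-half mix is an assumption; the documents give no case mix.

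**6. Precision after the fix.** With 40 pairs, the 95% interval for a mean change has half-width 2.02/sqrt(40) = 0.32 SD. If the SD were the MDADI pilot value, that is 0.32 x 23.68 = 7.6 points. No SD is given for the secondary measures.

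**The case against.** Section 4 calls the study exploratory and Part A descriptive. Summaries at baseline, 3 and 6 months are ordinary in such a study, and the main question, change in MDADI, is already paired. The missing baseline in the PSS-HN item looks like a drafting slip, since the other repeated functional measures name baseline and the data are collected. Nothing forbids pairing at analysis. A flow diagram and the number alive are already planned, so some attrition will be visible.

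Much of this stands, and it is why the point is modest. But the objective is worded as change, and nothing commits the analysis to measuring it. The flow diagram and survival count do not give the number measured per instrument at each visit, or the baseline scores of patients lost.

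A reader might infer more than the documents support:

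- *That loss would show as recovery.* The only trajectory in the documents is the pilot MDADI fall of 13.9 points, in 10 patients. At 20% loss, reversing a fall of that size needs D above 13.9/0.20 = 69.5 points. Only the most extreme cell of the table (16) exceeds 13.9. Blunting or masking is the supportable wording.
- *That about 40% of the cohort will die by 6 months.* Those survival figures cover platinum-treated patients. The cohort includes surgery and re-irradiation, and Section 1 also cites 50% five-year survival after surgery and better survival on pembrolizumab in selected patients.
- *That participants from identification centres shift the FEES case mix.* They are seen by video, so they have no FEES at any visit. This limits whom FEES represents, but only patients who change visit mode alter the group.
- *That secondary objective 1 covers UW-QoL.* It falls under secondary objective 2, which is to assess. The case for change in UW-QoL rests on the rationale in Section 2.

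**Conclusion.** The point holds as a low-cost improvement. The objective asks for change, PSS-HN has no baseline in its endpoint, and the planned secondary summaries do not separate change within patients from change in who is measured. The likely direction is towards understating decline.

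The size is illustrative: 2 to 4 points on a 0-100 scale at 20% loss and a 10 to 20 point deficit, both assumed. No size is shown for IDDSI (0-8), the WST (ml per second) or DIGEST (0-4). The primary comparison is already within patient, and the sample size reproduces; neither is challenged here.

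**What to change.** 1. In Section 6, add baseline to the PSS-HN endpoint.
2. In Sections 6 and 11, for PSS-HN, 100ml WST, IDDSI, FEES-DIGEST and (under the rationale in Section 2) UW-QoL, report within-patient change from baseline to 3 and to 6 months in patients with both values. Use mean change with a 95% confidence interval, or, for IDDSI and DIGEST, median change with the numbers better, the same and worse. Keep the visit summaries as supporting results.
3. Give the number measured for each instrument at each visit, the number with paired FEES, and the baseline scores of patients lost by 6 months. Report deaths alongside.

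The cost is wording in two sections and a little more analysis of data already collected, with no extra visits or patients. The downside is a smaller paired number. Paired change also still describes only patients who reach and can complete the later assessment; someone who becomes nil by mouth has no later WST. The counts and deaths in step 3 must therefore accompany it.
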